compared to Carbamazepine in healthy subjects employing a double-blind, two-period, crossover design. The design provides robust statistical strength and controls for selection bias created by individual variability in cognitive performance. The use of healthy subjects will control for the effect of changes in seizure frequency on cognitive function. In addition, examining AED cognitive effects in healthy subjects allows extrapolation of the results to other patient populations treated with AEDs (e.g., psychiatric and pain disorders).

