Urine Pregnancy tests will be performed on women of childbearing potential at Weeks -1, 10 & 20 (visits 1, 4 & 6).

In subjects of Asian descent, blood will be obtained to test for the HLA B\*1502 allele. If present, subjects will not receive drug or continue in the study. Subjects lost for this reason will be replaced by new enrollees.

Anticonvulsant blood levels will be collected at Weeks 6 and 16 (i.e., visits 3 & 5). Carbamazepine levels are to be sent to the hospital laboratory for immediate

analysis. The Eslicarbazepine and Carbamazepine levels will be sent to an outside contract lab. Results are to be reviewed and stored by the non-blinded investigator.

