## **X. STATISTICAL EVALUATION**

### **A. Sample Size**

Estimations based on an overall composite score (sustained attention and memory [SAM] + neuropsychological) for carbamazepine-levetiracetam (Meador et al, 2007) would predict that with a sample size of 30 subjects in a 2-period crossover study, the probability is 90% that the study will detect a treatment difference at a 2-sided 0.01 significance level, if the true difference between the treatments is 0.370 units. This is based on the assumption that the SD of the difference in the response variables is 0.490. Given an estimated dropout of 30% to 40%, the planned sample size needed to enroll is 40 to 45 subjects.

The SDMT is a neuropsychological measure that has been sensitive to AED effects in multiple studies. Based on the SDMT for carbamazepine vs. nondrug in the carbamazepine-levetiracetam study, a total of 31 subjects will need to complete the 2-period crossover study. The probability is 90% that the study will detect a treatment difference at a 2-sided 0.01 significance level, if the true difference between the treatments is 3.800 units. This is based on the assumption that the standard deviation of the difference in the response variables is 5.100. Given an estimated dropout of 30% to 40%, the study would need to enroll between 42 and 47 subjects.

Based on the above 2 scenarios, the planned sample size to enroll in this study is 46 subjects to complete 30.

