### **B. Methodology for statistical analysis**

The parameters of interest are listed in Section VII. Descriptive statistics will be used to provide an overview of the primary, secondary, and other variable results. For categorical parameters, the number and percentage of subjects in each category will be presented. The denominator for percentages will be based on the number of subjects appropriate for the purpose of analysis. For continuous parameters, descriptive statistics will include number of subjects, mean, standard deviation (SD), median, minimum, and maximum. Unless otherwise specified, baseline neuropsychological data will be based on the Visit 2 assessments.

The primary outcome (pharmacodynamic) variable will be analyzed as the within subject difference between drugs in the overall neuropsychological composite Z-score for CBZ vs. ESL comparing between end of Maintenance Period scores for each drug (ie, Treatment Period 1 to Treatment Period 2). The overall composite Z-score will be computed for each condition from the individual cognitive test scores from the computerized tests and non-computerized neuropsychological tests (including the behavioral questionnaires) after transformation to Z-scores. The Z-score will be calculated using the values (mean and SD) from the average of the scores from the 3 nondrug conditions (Baseline, first Washout Period, and second Washout Period).

The primary analysis will compare the composite Z scores for ESL to Carbamazepine

for each subject at the end of the Treatment Maintenance Periods. Since the analysis is based on an overall composite score, no correction for multiple comparisons is necessary. The use of composite Z-scores avoids Type II error.

Secondary analyses will be conducted to compare the two AEDs states to the non-drug average from Visits 2, 4 & 6. The initial cognitive assessment (i.e., Visit #1) is given to reduce practice effects and will not be used in the statistical analyses. Secondary analyses will also be conducted comparing the 2 drug states to each other and the non-drug state for the individual neuropsychological variables.

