Summary statistics will be calculated by treatment for each evaluation of antiepileptic blood levels (ABLs). Additional analyses of data will be performed which take the ABLs into account. Linear correlations of plasma concentrations and the overall composite and individual score variables will be plotted with a fitted regression line superimposed for each drug condition.

The incidences of all adverse events reported during the trial will be tabulated by treatment and study period. The other safety variables, which include changes in hematology, clinical chemistry, and urinalysis parameters, and vital signs will be analyzed descriptively. The actual measurement and its change from Baseline will be presented by visit and period of collection. In addition, shift tables may be used to evaluate the number and percentage of subjects having a different post-Baseline status when compared with their Baseline status.

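### The one specified plasma-level analysis uses the on-drug score without the subject's own nondrug average, which weakens any exposure relation it could show

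*Combined protocol and SAP*

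**What the plan says.** Blood levels come once per drug: "Anticonvulsant blood levels will be collected at Weeks 6 and 16" (section IX, laboratory assessments), the visits at the end of each maintenance period. Section X.B then sets out the exposure analysis: "Linear correlations of plasma concentrations and the overall composite and individual score variables will be plotted with a fitted regression line". The two drugs are kept apart, with a separate line in each. The section names neither a change score nor a nondrug covariate here. The sentence before it is open-ended: "Additional analyses of data will be performed which take the ABLs into account".

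Elsewhere X.B does use the nondrug state as a reference: "Secondary analyses will be conducted to compare the two AEDs states to the non-drug average from Visits 2, 4 & 6". It also standardises the scores on nondrug data: "The Z-score will be calculated using the values (mean and SD) from the average of the scores from the 3 nondrug conditions". It does not say whether that mean and SD are group values or each subject's own.

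Section I gives as a reason for the crossover that it "controls for selection bias created by individual variability in cognitive performance".

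**The concern.** Within one drug there is one point per subject, so the fitted line compares people with each other. The spread of on-drug scores then holds three things: stable ability, session noise and any exposure effect. Only the last is of interest. The crossover removes stable ability from the primary comparison. The plasma-level analysis leaves it in, although the data needed to take it out are collected and already averaged for another analysis.

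At stake is how the plot is read. A real relation between level and score could look flat and be reported as no relation to blood level.

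**Working it through.** **The plan's own figure.** X.A states that "with a sample size of 30 subjects in a 2-period crossover study, the probability is 90" per cent for a difference of 0.370 with SD of the difference 0.490 at two-sided 0.01. A paired t-test with the noncentral t gives power 0.906 at n = 30, and 30 is the smallest n that reaches 90%. The figure reproduces. The plan gives no figure for the plasma-level analysis, so n = 30 is carried over.

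**Assumptions (none is in the documents).** Single-session variance is 1. Exposure adds variance 0.05 to the on-drug score. Concentration is unrelated to ability. Retest correlation between any two sessions is ρ. All three nondrug visits are present.

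**Outcome variance apart from exposure, V.**
- Score itself: V = 1.
- Change from the three-visit average: V = (1 − ρ)(1 + 1/3).
- Average as covariate: the average has variance (1 + 2ρ)/3 and covariance ρ with the on-drug score, so V = 1 − 3ρ²/(1 + 2ρ).

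The correlation is r = √(0.05/(V + 0.05)). Power by Fisher z is Φ(atanh(r)·√27 − 1.96).

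Score itself, at any ρ: r = √(0.05/1.05) = 0.22, power 21%.

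| ρ | V, change | r (power), change | V, covariate | r (power), covariate |
|---|---|---|---|---|
| 0.25 | 1.000 | 0.22 (21%) | 0.875 | 0.23 (23%) |
| 0.5 | 0.667 | 0.26 (29%) | 0.625 | 0.27 (31%) |
| 0.7 | 0.400 | 0.33 (44%) | 0.388 | 0.34 (45%) |
| 0.8 | 0.267 | 0.40 (59%) | 0.262 | 0.40 (60%) |
| 0.9 | 0.133 | 0.52 (85%) | 0.132 | 0.52 (86%) |

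Using √26 to charge for the covariate lowers its powers by at most 2 points (23%, 30%, 43%, 58%, 84%).

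**Break-even.** (1 − ρ)(4/3) = 1 at ρ = 0.25. Below that, the simple change score is noisier than the score itself. The covariate form has V ≤ 1 at every ρ, so apart from the one degree of freedom it does not lose.

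**A larger effect, in the plan's units.** Take half of 0.490² as single-session residual variance: 0.2401/2 = 0.120. The change score then has variance 0.120 × 4/3 = 0.160 (SD 0.400), and the on-drug score 0.120/(1 − ρ). Suppose the correlation on the change scale is 0.50 (power 81%). Exposure variance is 0.160 × 0.25/0.75 = 0.053. On the score itself r = √(0.053/(0.120/(1 − ρ) + 0.053)), which is 0.43, 0.34, 0.29 and 0.21 at ρ = 0.5, 0.7, 0.8 and 0.9 (power 66%, 46%, 33%, 19%). The 5% critical value at n = 30 is 0.361. The 0.490 cancels from these correlations, so they depend on ρ alone.

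**The case against.** **The Z-score may already be a change score.** If its mean is each subject's own nondrug mean, a Z-scored outcome is already a deviation from nondrug, and the point fails for the composite. The wording leans the other way. A subject has only one average over the three conditions, so an SD of that average exists only across subjects. Group values shift and rescale everyone alike and leave a correlation for any one test unchanged. But X.B does not settle it, and it should.

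**The plan is not limited to these plots.** A reader might infer that this is the trial's only check on exposure. The sentence on additional analyses rules that out. Those analyses are unspecified, so they cannot be credited as a remedy. The accurate statement is that this is the only specified one.

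**Swamping is not shown.** A reader might infer that ability differences drown any exposure effect. The documents give no retest correlation or between-subject SD. Over ρ of 0.5 to 0.8, a correlation of 0.50 falls to 0.43 to 0.29, which is attenuation and not elimination. With the smaller assumed effect, the adjusted analysis still has less than even power at ρ of 0.7 or below, so much of the limit is n = 30.

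**Confounding by age.** It is tempting to add that age could drive both clearance and cognition in an 18 to 55 sample. The documents say nothing about age and clearance of either drug, so this is not part of the point.

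**The analysis is exploratory.** X.B attaches no hypothesis, alpha or decision rule to the plots, and the 0.05 test above is only a yardstick. This stands and sets the severity.

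**Conclusion.** The point holds as a low-severity improvement. The specified exposure analysis ignores a nondrug reference that the plan already computes and, on the group-referenced reading of the Z-score, is weaker than it need be. The gain from adjustment depends on a retest correlation that the documents do not give: close to nothing at 0.25 (0.22 to 0.23), moderate at 0.7 (0.22 to 0.34) and large at 0.9 (0.22 to 0.52), all under the assumed exposure variance of 0.05. A simple change score does about as well as the covariate from 0.7 upward but loses below 0.25. The reliabilities of the individual tests are not given, so the covariate is the safer choice. Nothing here touches the primary within-subject comparison of the two drugs.

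**What to change.** In X.B, for each drug, regress the on-drug composite and each individual score on plasma concentration with the subject's nondrug average as covariate, and plot the adjusted relation with its fitted line. Define that average as the mean of the Visit 2, 4 and 6 scores that are available. Subjects who leave early then stay in, and nothing is imputed, which fits section X.D. Also state in X.B that the Z-score mean and SD are group-level values.

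The cost is wording, one extra covariate, and a noisier average for subjects with fewer nondrug visits. With m visits V = 1 − ρ²/(ρ + (1 − ρ)/m). At ρ = 0.7, if every subject had only one visit, V = 1 − 0.49/1 = 0.51 and r = √(0.05/0.56) = 0.30. That is below the 0.34 with three visits but still above the 0.22 without adjustment. No new data are needed. The change should be made before unblinding.

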**E. Visit-Specific Treatment and Evaluation Sequence**

Subjects will be randomly assigned to receive both AEDs, for 6 weeks each, in a random sequence of administration. Each AED treatment period will be followed by a 3-day taper period and a 25-day washout period.

At all visits, subjects will be advised on drug compliance and avoidance of medications which may adversely effect the results of cognitive function testing. Adverse events will be documented on the appropriate case report form. Appointments will be made for follow up

visits and care will be taken to schedule all cognitive and behavioral function testing for a given subject at the same time of the day. Testing will be in the approximately 2 hours post morning dose. The time of testing and time of last 2 doses will be recorded.

The timetable for the study is listed in Appendix A. This is a visit-by-visit description of the events scheduled for each visit.

**Visit 1**      Screening Visit (-1 week prior to randomization)

Subjects will be screened to assure they meet all of the inclusion criteria and none of the exclusion criteria. All eligible subjects will be required to give informed consent. A complete history, physical examination, neurologic examination, laboratory screening including urine pregnancy test (if woman of child bearing potential), HLA B\*1502 testing for subjects of Asian descent, IQ screen with Peabody Picture Vocabulary Test, and full cognitive battery (see below) will be obtained.

**Visit 2**      Randomization- Drug Period 1 (Study week 0)

At this visit all subjects who had successfully completed all screening tests and had no significant abnormalities on baseline laboratory, physical exam, neurologic exam, or IQ testing will be randomized to study drug. At this visit, neuropsychological testing will be conducted before the first dose of study drug is administered. Subject will be randomized, and study drug will be dispensed.

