**Study weeks 2 - 6**

During this period, subjects will titrate up during the 1st two weeks, and be maintained on 800mg/day of ESL or Carbamazepine during weeks 3-6. The subject's doses will be titrated according to the schedule outlined below. Telephone contacts will be made at weeks 2 and 4 to check on adverse events and to encourage compliance.

**Visit 3**      (Study week 6)

At this visit, pill bottles will be checked, and pill counts conducted. Vital signs and a brief physical examination will be obtained. In addition, antiepileptic drug blood levels, CBC and chemistries will be obtained, and cognitive function and behavioral testing will be performed. (Cognitive function and behavioral testing will be rescheduled if the subjects inadvertently used alcohol, non-approved drugs 72 hours before testing.)

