**Study weeks 6 - 10**

The subject will be tapered off drug over the first 3 days and then remain off drug for the next 25 days.

**Visit 4**      (Study week 10)

This visit ends the washout period and begins the baseline for Drug Period 2. At this visit, vital signs and a brief physical examination will be obtained. Subjects will undergo cognitive and behavioral testing and then the alternate drug treatment will be dispensed. Titration will be similar to the first titrations beginning at Visit 2. In addition, a pregnancy test will be obtained in women of child bearing potential.

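### Laboratory, vital-sign and shift-table displays are specified without a treatment split, so as written they would mix ESL and carbamazepine at each on-drug visit

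*Combined protocol and SAP*

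**What the plan says.** Section X.B (Methodology for statistical analysis) sets a separate grouping rule for each kind of data.

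- **Blood levels:** "Summary statistics will be calculated by treatment for each evaluation of antiepileptic blood levels (ABLs".
- **Adverse events:** "The incidences of all adverse events reported during the trial will be tabulated by treatment and study period".
- **Remaining safety variables:** "The other safety variables, which include changes in hematology, clinical chemistry, and urinalysis parameters, and vital signs will be analyzed descriptively". The display rule follows: "The actual measurement and its change from Baseline will be presented by visit and period of collection".
- **Shift tables:** "shift tables may be used to evaluate the number and percentage of subjects having a different post-Baseline status when compared with their Baseline status". They are optional, and no grouping factor is given.

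On the design, section VI.E states: "Subjects will be randomly assigned to receive both AEDs, for 6 weeks each, in a random sequence of administration". It gives no allocation ratio. The scheduled on-drug clinic visits are Visit 3 (week 6) and Visit 5 (week 16), both with vital signs and blood work; for Visit 3 the text reads "In addition, antiepileptic drug blood levels, CBC and chemistries will be obtained, and cognitive function and behavioral testing will be performed". Visit 4 is off drug: "This visit ends the washout period and begins the baseline for Drug Period 2".

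The only baseline definition in X.B is Visit 2, and it is given for neuropsychological data.

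**The concern.** The trial compares two drugs, and section I gives differential side effects as a main reason for such comparisons. In a crossover with random order, neither visit nor period identifies the drug a subject is taking. A laboratory or vital-sign table grouped by those two factors alone would therefore show an average over both drugs at each on-drug visit. A change confined to one drug would look like a smaller change present in both periods, and the difference between drugs would not be visible.

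A second gap lies in the same sentence. It refers to change from Baseline, but no Baseline is defined for safety variables. Appendix A shows blood work at screening, at the two on-drug visits and at the final visit, and none at Visit 2.

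**Working it through.** No figure in the plan bears on this point, so there is nothing to reproduce. The check is a comparison of texts, followed by a short calculation of what pooling does.

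**1. Is treatment implied by period?** The adverse-event rule names treatment and study period as two separate factors, so period alone does not stand for drug there. Elsewhere the numbered periods are chronological: Drug Period 1 starts at Visit 2, Drug Period 2 starts at Visit 4, and Appendix A has a first and a second drug period. With random order, each period contains both drugs. No other section adds a by-drug display for laboratory or vital-sign data.

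**2. Effect on means.** Let p be the share of subjects on ESL in Period 1. Let dE and dC be the mean changes caused by ESL and carbamazepine. Assume no dropout and no period effect.

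- Visit 3 mean = p·dE + (1 − p)·dC
- Visit 5 mean = (1 − p)·dE + p·dC
- Visit 5 minus Visit 3 = (2p − 1)·(dC − dE)

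Take dE = 0 and dC = 1 unit as an illustration:

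| p (assumed) | Visit 3 | Visit 5 | Visit 5 − Visit 3 | Same data by treatment (ESL, carbamazepine) |
|---|---|---|---|---|
| 0.4 | 0.6 | 0.4 | −0.2 | 0, 1 |
| 0.5 | 0.5 | 0.5 | 0 | 0, 1 |
| 0.6 | 0.4 | 0.6 | 0.2 | 0, 1 |

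With equal sequences, a shift D on one drug appears as D/2 at both visits. With unequal sequences, a remnant of the drug difference appears between visits and would be read as a period effect.

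**3. Effect on shift tables, if they are grouped by visit.** Assume 30 completers, 15 per sequence, and illustrative shift rates of 20% on one drug and 0% on the other. At each on-drug visit, 15 subjects take the affected drug, giving 15 × 0.20 = 3. The table shows 3/30 (10%) at Visit 3 and 3/30 (10%) at Visit 5. By treatment, the same data read 6/30 (20%) and 0/30 (0%).

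**4. Which parameters are affected?** Pooling arises only where there is an on-drug value, and the documents differ on what is measured then.

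- The Visit 3 and Visit 5 descriptions list CBC and chemistries without restriction.
- Section IX.B.2 limits chemistry at those visits to SGOT and SGPT.
- Appendix A, footnote b, limits blood work there to CBC, SGOT and SGPT.
- None of these schedules urinalysis at an on-drug visit.

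On the narrower schedule, the point covers CBC, two liver enzymes and vital signs.

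**The case against.** The strongest reply is that pooling is inferred from silence. X.B does not say the drugs will be combined and does not forbid a split. Its term for the collection period is undefined. In describing the primary comparison, X.B pairs the scores for each drug with Treatment Periods 1 and 2, which is a loose use of period for drug. Each drug period also has a single on-drug visit, so naming both visit and a purely chronological period is redundant there. This shows that the author may have intended a by-drug display. It does not supply one: the written rule lists its grouping factors and treatment is not among them, although it is named for adverse events and blood levels in the same section.

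A reader might infer two stronger things that the documents do not support.

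- *All on-drug safety reporting pools the drugs.* It does not, because adverse events are tabulated by treatment and study period.
- *The trial could not tell which drug was associated with a change.* The gap is in the planned display and not in the data. Each subject's sequence is known, so a by-drug table can be made at any time. Nor would a descriptive table by treatment establish cause.

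It is also fair to say that these displays carry no test and that the stated objective is cognitive and behavioral. That limits how much weight the point deserves.

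**Conclusion.** The point holds in a limited form. As written, X.B groups laboratory and vital-sign values by visit and period without treatment and leaves the optional shift tables with no stated grouping. Followed literally, the rule for values combines ESL and carbamazepine subjects at Visits 3 and 5.

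The halving of a one-drug shift rests on equal sequence sizes, no dropout and no period effect. The documents state no ratio, and section X.A expects 30% to 40% dropout, which could change the drug mix at Visit 5. Other splits change the figures but do not recover the drug contrast. The 20% and 0% rates are illustrative only.

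The reach is confined to descriptive displays of parameters measured on drug, and it depends on which laboratory schedule applies. Severity is minor, and the correction is a free improvement.

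**What to change.** 1. In X.B, replace the grouping rule for these variables with: *by treatment at the time of collection (ESL, carbamazepine, nondrug), visit and period*. Keep visit in the rule. Without it, a nondrug category could merge pre-treatment values with washout values, such as vital signs at Visits 2 and 4.
2. Apply the same split to any shift tables.
3. State which visit is the safety Baseline, separately for blood work and vital signs if they differ, and whether Period 2 has its own. Appendix A shows no blood work at Visit 2 or Visit 4, while the heading of IX.B.2 lists week 10. The laboratory schedule must therefore be reconciled before a Period 2 laboratory baseline can be named.

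The cost is two or three sentences in X.B and an added grouping variable in the table programs. Steps 1 and 2 need no new data or visits. Step 3 needs none either, provided the Baseline chosen is a visit at which the measurement is already taken.
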